1.0 OBJECTIVES

1.1 To determine the efficacy of intravenous busulfan, dose targeted to achieve AUC of 700-900 combined with fractionated total body irradiation and VP16 as a preparative regimen for marrow transplantation from an HLA-identical sibling in patients with advanced hematological malignancies (AML or ALL) beyond 2nd remission, induction failure, in relapse, chronic myelogenous leukemia in blast crisis and myelodysplasia (RAEB and RAEBIT).

Rev. 6/13/02 1.2 To determine the efficacy of this regimen in patients with AML in first remission with unfavorable cytogenetics.

1.3 To evaluate the early and late toxicities of this regimen.

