
FTBI and VP-16 in an attempt to decrease the relapse rate in those patients transplanted for advanced hematological malignancies. The rationale behind the study was that we combined three non-cross resistant anti-leukemic agents with non-overlapping extramedullary toxicities. An in vitro synergy has been demonstrated between busulfan/VP-16 and busulfan/VP-16 has been proven to be an effective regimen for relapsed leukemia and for ABMT for AML in first and second remission.^{23,24} The dose limiting toxicity occurred at 12mg/kg the MTD was defined at 11mg/kg. At this dose level median first dose AUC for these patients was 892 μ M*min (460-1267). With a median follow-up of 11.5 months, the disease-free survival is 32%, and the probability of relapse is 40%. The only variable predictive of a disease-free survival and relapse was the busulfan dose of 7-8 mg/kg. In this phase I study there was a wide variability of the AUC of busulfan due to the variability of absorption of oral busulfan. An AUC of 700-950 showed a trend to a decreased relapse rate and improved disease free survival.

A phase II study utilizing IV busulfan was conducted at City of Hope which has resulted in FDA approval of IV busulfan and it is proposed to substitute IV busulfan which has been shown to have more predictable pharmacokinetic properties than the oral preparation resulting in a better toxicity profile.^(25,26,27)

Rev. 6/13/02

*Patients with AML in first complete remission (CR1) with unfavorable cytogenetics have a relapse rate of 40% with our current transplant regimen consisting of fractionated radiation and etoposide. We propose to use this new preparative regimen to see if it can improve the DFS and relapse rate for this subset of patients with AML in first CR.

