5.0 ELIGIBILITY CRITERIA

5.1 Inclusion Criteria

- 5.1.1 Patients with acute myelogenous or lymphocytic leukemia who are not in first remission or second remission i.e. after failing remission induction therapy or in relapse or beyond second remission, or patients with chronic myelogenous leukemia in blastic phase of the disease are eligible for the study. Patients with refractory anemia with excess blasts and in transformation will be eligible.
- 5.1.2 All candidates for this study must have a HLA (A,B,C,DR) identical siblings who is willing to donate bone marrow for marrow grafting. All ABO blood group combinations of the donor/recipient are acceptable since even major ABO compatibilities can be dealt with by various techniques. (Red cell exchange or plasma exchange). Peripheral blood stem cells or bone marrow can be used.
- 5.1.3 Prior therapy with VP-16 and busulfan is allowed.
- 5.1.4 Patients must be older than 16 and the upper age limit is physiological age of 50.
- 5.1.5 A cardiac evaluation with electrocardiogram and MUGA or echocardiogram is required in all patients. Patients must have an ejection fracture of greater than or equal to 50%.
- 5.1.6 Patients must have a serum creatinine of less than or equal to 1.2 or creatinine clearance $> 80\text{ml/min}$.
- 5.1.7 A bilirubin of less than or equal to 1.5. Patients should also have an SGOT and SGPT less than 5 times the upper limit of normal.
- 5.1.8 Pulmonary function tests including DLCO will be performed. FEV₁ and DLCO should be greater than 50% of predicted normal value.

5.1.9 The time from the last induction or reinduction attempt should be greater than or equal to 28 days.

5.1.10 Signed informed consent form approved by the IRB is required. The patient, family member and transplant staff physician (physician, nurse, and social worker) meet at least once prior to starting the transplant procedure. During this meeting all pertinent information with respect to risks and benefits to donor and recipient will be presented. Alternative treatment modalities will be discussed. The risks are explained in detail on the enclosed consent forms.

Revised 8/28/00

Revised 3/11/02

Revised 6/13/02

5.1.11 Patients with AML in first remission with poor risk cytogenetics (11q abnormalities, -7,-5, complex abnormalities i.e. > 3 abnormalities, 6;9 translocation and 3q abnormalities del (7q), del (5q), complex abn ≥ abnormalities, 9q, 20q, 21q, 17p, t(9;21)).

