12.0 STATISTICAL CONSIDERATIONS

- 12.1 Primary and Secondary Endpoints: The primary endpoint of the Phase II study is to evaluate the efficacy of FTBI/BU/VP-16 with a targeted Busulfan dose of AUC 700-900 as a preparative regimen for allogeneic BMT in patients with advanced hematological malignancies (AML or ALL beyond second remission, in induction

failure, or in relapse; CML in blast crisis; and myelodysplasia, RAEB and RAEBIT). Secondary endpoints will include early and late toxicities of this regimen.

Efficacy will be estimated based on 2 and 5 year disease-free survival (DFS). The effects of cytogenetics, WBC at presentation, and number of courses of induction therapy to achieve remission will be evaluated as possible prognostic factors for relapse, DFS, and overall survival.

- 12.2 Sample size Estimation and Length of Accrual: A total of 50 patients with advanced malignancies and less than 50 years old (physiological age) will be accrued to this trial, so that in estimating the engraftment and relapse rates the maximum standard error will be 0.7. We expect to accrue approximately 10-12 patients per year so that this trial will require 4-5 years of completion.
- 12.3 If at any time the severe treatment related complication rate (e.g. severe VOD, interstitial pneumonia, neurotoxicity at day 100 post BMT) or regimen related mortality exceeds 20% with a high probability (i.e. >95%) then further accrual to the trial will be terminated. This would occur if the following numbers of events have been observed, monitoring after every set of 10 patients is accrued:

| Number of Patients Accrued | Number of Events Leading to Early Termination |
|-------------------------------|--|
| 10 | 5 |
| 20 | 8 |
| 30 | 11 |
| 40 | 14 |

12.4 **Statistical Analyses:** The rate of engraftment and median time to engraftment will be estimated, defined as time to ANC > 500 and platelets >20,000.

The Kaplan-Meier method will be used to estimate time to relapse, DFS, and overall survival, and 95% confidence intervals will be calculated using Greenwood's variance.

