The intent-to-treat group will include all patients receiving the preparative regimen for BMT. For overall survival, failure time will be calculated from the day of first treatment to the day of death due to any cause for those patients who fail. For DFS, the failure time will be calculated from the day of first treatment to the day of disease relapse or death due to any cause. For patients who remain alive and well at the time of analysis, the survival time will be censored as of the date of last contact. The Cox proportional hazard regression model will be used to analyze possible prognostic factors for relapse, DFS and overall survival.

Revised
9/26/00

12.5 Patients with AML with unfavorable cytogenetics will be a subset analysis that will include approximately 12 patients. This number is too small for formal hypothesis testing. It will give us some experience with this population of patients and descriptive analysis will be used along with estimation of relapse rate and 95% C.I.

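### The only analysis set in 12.4 takes in first-remission AML, while 12.1 and 12.2 define the primary DFS question and the 50 patients as advanced disease

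*Combined protocol and SAP*

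**What the plan says.** - **Primary question (12.1).** The regimen is assessed as a "preparative regimen for allogeneic BMT in patients with advanced hematological malignancies", followed by a closed list: AML or ALL beyond second remission, in induction failure or in relapse; CML in blast crisis; RAEB and RAEBIT. First-remission AML is not on the list. Efficacy is measured by 2- and 5-year DFS.
- **Size (12.2).** "A total of 50 patients with advanced malignancies", justified by a maximum standard error for engraftment and relapse rates, with accrual of 10-12 a year over 4-5 years.
- **Analysis set (12.4).** "The intent-to-treat group will include all patients receiving the preparative regimen for BMT". There is no restriction by disease status and no second set. The Kaplan-Meier estimates and Cox models follow from it.
- **The other group.** Criterion 5.1.11 admits "Patients with AML in first remission with poor risk cytogenetics". Objective 1.2 is "To determine the efficacy of this regimen in patients with AML in first remission with unfavorable cytogenetics", and the Background wants "to see if it can improve the DFS and relapse rate for this subset of patients with AML in first CR".
- **What is planned for that group (12.5).** "Patients with AML with unfavorable cytogenetics will be a subset analysis that will include approximately 12 patients"; "descriptive analysis will be used along with estimation of relapse rate and 95% C.I".

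**The concern.** The primary question and the analysis set cover different populations. One analyst could follow 12.1 and report DFS for advanced disease. Another could follow 12.4 and report DFS for everyone treated. Both could cite the plan. The second estimate would not answer 12.1, and it would probably be higher: the Background puts long-term disease-free survival at about 50-70% for transplant in first remission or chronic phase, against 10-40% for a successful outcome in later disease.

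Section 12.5 does not settle this. It does not take the roughly 12 patients out of the main curves, and it does not say whether they count toward the 50. It names a relapse rate but no DFS, although the Background states the aim for this group in terms of both.

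A smaller gap sits in the same section. Patients in induction failure or relapse are eligible, so some may never reach remission as 10.2 defines it. Section 12.4 counts relapse or death as DFS events and censors patients who are alive and well. A patient alive with leukemia that never remitted fits neither rule.

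**Working it through.** **1. The plan's own figure.** The maximum standard error (SE) of a proportion is sqrt(0.25/n). For n = 50 this is 0.0707, so the 0.7 printed in 12.2 does not reproduce. It looks like a decimal slip for 0.07, which needs 0.25/0.07² = 51.0 patients. This is a separate correction.

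**2. Are the 12 inside the 50?** 50/12 = 4.2 and 50/10 = 5.0 years, matching the stated 4-5. 62/12 = 5.2 and 62/10 = 6.2 years, which does not match. This leans toward inside, but the accrual figure may simply not have been updated. Both cases are carried below.

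**3. Inputs for the DFS shift.**
- Advanced DFS, a: 32% (Background, phase I of this combination with oral busulfan, median follow-up 11.5 months) or 20% (Background, randomized cooperative-group study of other regimens).
- First-remission DFS, c: not given for unfavorable cytogenetics, so 40-70% is an assumption. 70% is the top of the Background's general range. 60% is 1 minus the 40% relapse rate on the current regimen, with no non-relapse deaths. 40% also subtracts 20% non-relapse mortality, a figure borrowed from the 12.3 safety threshold, which is a limit and not an estimate.
- All 12 patients are taken as first remission. Fewer would give a smaller shift.

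Shift = w × (c − a), with w = 12/62 = 0.194 if additional and 12/50 = 0.24 if within. SE = sqrt(a(1 − a)/n) for the advanced group, n = 50 or 38, ignoring censoring.

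| a | The 12 are | SE | c = 40% | c = 60% | c = 70% |
|---|---|---|---|---|---|
| 32% | additional | 0.066 | +1.5 points (0.23 SE) | +5.4 (0.82) | +7.4 (1.11) |
| 32% | within | 0.076 | +1.9 (0.25) | +6.7 (0.89) | +9.1 (1.21) |
| 20% | additional | 0.057 | +3.9 (0.68) | +7.7 (1.37) | +9.7 (1.71) |
| 20% | within | 0.065 | +4.8 (0.74) | +9.6 (1.48) | +12.0 (1.85) |

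**4. First-remission DFS that moves the estimate by one SE**, c = a + SE/w: 66.1% (additional) or 63.5% (within) at a = 32%; 49.2% or 47.0% at a = 20%.

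**5. Relapse.** Shift = w × (0.40 − r), with advanced relapse r = 40-70% from the Background: 0 to −5.8 points (additional) or 0 to −7.2 (within). It is zero if both groups relapse at 40%.

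**6. Precision once the groups are separated.** Maximum SE for advanced disease is sqrt(0.25/50) = 0.071 if the 12 are additional and sqrt(0.25/38) = 0.081 if within. For the 12 alone it is 0.144; 6 of 12 gives an exact 95% interval of 21-79%.

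**The case against.** The best answer is that section 12 should be read as a whole. Section 12.1 lists the primary population, 12.2 repeats it, 12.4 only separates treated from untreated patients, and 12.5 gives the remaining group its own descriptive analysis. On intent this is right. It does not remove the conflict, because 12.4 is the text an analyst applies, it sets no disease limit, and calling the 12 a subset suggests they stay inside the overall group.

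A reader might also infer that 12.5 deliberately mixes first-remission AML with relapsed AML carrying unfavorable cytogenetics, since it does not mention remission. The documents do not support that: Objective 1.2 and the Background both use the phrase for first-remission AML. The wording is loose, but the meaning is fairly clear.

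On size, two stronger readings are tempting. One is that first-remission DFS cannot exceed 60%, so at an advanced DFS of 32% the shift always stays under one SE. But the 40% relapse rate behind that figure belongs to the current regimen, which this trial hopes to improve on, so 60% is no ceiling. The other is that pooling distorts the result by more than one SE. That holds only above the thresholds in step 4 of the working, and no document gives a DFS for this group.

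It is also fair to say that no hypothesis test, DFS benchmark or decision rule uses the estimate. That limits the severity.

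**Conclusion.** The conflict stands. Followed literally, 12.4 yields a DFS estimate that does not answer the question in 12.1, so this is a wrong rule and not just missing detail. It should be fixed, although the intent is recoverable from 12.1 and no formal test is affected.

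The plausible effect runs from under a quarter of an SE to nearly two. The range rests on an assumed first-remission DFS of 40-70% and on all 12 patients being in first remission; it illustrates the effect and does not bound it. The relapse estimate may not move at all.

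The gap for patients who never attain remission is real but secondary, and no size is claimed for it. A reader might take the day-100 marrow in Appendix VI as settling when to assess them. The documents do not support that: no section makes day 100 a remission cutoff. The calendar's columns are also misaligned in the extracted text (counting across puts the graft on Day 3, whereas 6.2 has Day 0), so the day-100 entry itself needs checking.

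**What to change.** - **12.4.** Add: *Primary DFS, overall survival and relapse estimates use regimen-treated patients with advanced disease (5.1.1) only; AML in first remission (5.1.11) is reported separately under 12.5.* Either restrict the Cox models in the same way or include disease status in them.
- **12.5.** Name the subset as AML in first remission with unfavorable cytogenetics. Add a descriptive DFS estimate with a 95% confidence interval beside the relapse rate.
- **12.2.** State whether the 12 are within or additional to the 50, and give the maximum SE for the advanced group to match: 0.081 for 38 or 0.071 for 50.
- **Appendix IX.** Add an eligibility-group field. Item 1 now requires that acute leukemia not be in first or second remission, and the form has no entry for 5.1.11.
- **Secondary, 12.4.** Count persistent disease as a DFS failure and do not censor it. The investigators should set the assessment date; the day-100 marrow is a candidate once the Appendix VI table has been checked.

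**Cost.** A few sentences and one form field, with no added patients; no added visits if an already scheduled marrow serves as the assessment. The headline DFS will probably be lower and its interval possibly wider. The first-remission estimate will stay imprecise and can only be descriptive.

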APPENDIX I
IV BUSULFAN KINETICS FORM

IRB#: _____
PATIENT _____
Medical Record #_____
MD/Pager # _____
Coordinator/Pager #_____

DATE: _____ (CIRCLE WEIGHT USED)
DOSE #: _____ Actual Body Weight _____
Start time: _____ Ideal Body Weight _____
Stop Time: _____ Adjusted IBW _____
DOSE: _____ mg

INFUSION TO RUN OVER 2 HOURS

| Tube # | Collection Schedule | Proposed Collection Time | Actual Collection Time |
|--------|--|--------------------------|------------------------|
| 1 | Immediately prior to beginning of infusion | APPROX. 0555 | |
| 2 | Immediately prior to end of infusion | APPROX. 0755 | |
| 3 | 15 minutes post infusion | APPROX. 0815 | |
| 4 | 30 minutes post infusion | APPROX. 0830 | |
| 5 | 60 minutes post infusion (1 hour) | APPROX. 0900 | |
| 6 | 180 minutes post infusion (3 hours) | APPROX. 1100 | |
| 7 | 240 minutes post infusion (4 hours) | APPROX. 1200 | |
| | | | |
| | | | |

** ALL samples to be obtained in 7cc green top tubes (Sodium Heparin) and kept on ice at Nurses Station.

Then send to Clinical Pathology.

RN SIGNATURE _____

Appendix II

FRACTIONATED TOTAL BODY IRRADIATION SCHEMA

| Session | Day | Time | Beam Direction | Energy (MeV) | Dose (rads) | Notes |
|---------|-----|------|----------------|-------------------|-------------|----------------------------------|
| 1 | -7 | 0730 | AP AP | 8/10X Electron | 120 | TLD Testes male (ALL only) |
| 2 | -7 | 1200 | AP | Electron | 400 | TLD |
| 3 | -7 | 1630 | PA | 8/10X | 120 | |
| 4 | -6 | 0730 | AP | 8/10X | 120+ | (PA Chestwall Boost) 300 |
| 5 | -6 | 1200 | PA | 8/10X | 120+ | (AP Chestwall Boost) 300 |
| 6 | -6 | 1630 | AP | 8/10X | 120 | |
| 7 | -5 | 0730 | AP | 8/10X | 120 | |
| | | | AP | electron | 300 | Chest wall boost |
| 8 | -5 | 1200 | PA | 8/10X | 120+ | (PA Chestwall Boost -300) |
| 9 | -5 | 1630 | PA | 8/10X | 120 | |
| 10 | -4 | 0730 | PA | 8/10X | 120 | |

Photon dose is calculated at mid-depth, central axis. Electron chest wall dose is calculated at 90% isodose level, where electron energy is selected to place 90% isodose level at pleural surface. At the first AP and PA sessions for total body irradiation, portal films with the treatment beam will be obtained prior to treatment to assure proper lung block placement. The x-ray total body irradiation dose given during portal film will be subtracted from the total dose planned for that session. Subsequent placement of lung blocks at the remaining sessions will be documented by verification films obtained during the actual treatment.

During the first AP and PA sessions for total body irradiation, the radiation dose received by the patient will be monitored by means of thermoluminescent dosimeters placed on the anterior surface of the patient's skin at the following anatomic locations: forehead, suprasternal notch, xiphoid process, umbilicus, pelvis, mid-thigh, knee, mid-calf, and ankle. The midline dose to the patient can be calculated from the sum of entrance and exit doses recorded by the thermoluminescent dosimeter. If thermoluminescent dosimeter indicates a deviation of greater than $\pm 10\%$ in the planned dose, either the compensating filter, the machine monitor units, or both may be modified for subsequent sessions.

Appendix III

- 1). **G-CSF Administration to Donors:** All donors will receive G-CSF 10 µg/kg/day for 6 consecutive days from day -5 to day 0. G-CSF will be administered by a subcutaneous injection daily beginning 5 days prior to day 0 (defined as the day marrow would ordinarily be given).
- 2). **PBSC Collection:** Donors may undergo vein to vein collections or may receive an appropriate catheter inserted on or before day of the treatment regimen. Donors will receive -5 daily doses of G-CSF, 10µg/kg/day by subcutaneous injection commencing on day -5. These doses will be administered each day in the Outpatient Department or at home.

Treatment Schema for Donor

| Days | -5 | -4 | -3 | -2 | -1 | 0 |
|------------------|-----------|-----------|-----------|-----------|-----------|----------|
| G-CSF 10µg/kg/SQ | X | X | X | X | X | |
| PBSC Collection | | | | | X | X |

PBSC's will be collected in the afternoon of day -1 and reinfused on day 0. *If the collection on day -1 contains less than 5.0×10^6 CD34+ cells per kg recipient weight, a second collection will be performed the following morning and transfused on day 0.

If PBSC's cannot be collected by a vein to vein technique, a percutaneous Mahurkar catheter will be inserted.

General procedures will include the use of a standard apheresis machined (COBE Spectra, Lakewood Colo.), and processing up to 16 l of whole blood during the collection. (Refer to Standard Practice Manual for collection procedure).

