6.2 Preparative Chemotherapy Regimen

Rev. 8/12/02

* Patient to sign consent form before starting Dilantin.

Rev. 11/8/01

Friday/Day -18

Begin dilantin 300mg/p.o. t.i.d. times 1 day, then 300mg/p.o./IV daily times 14 days.

Tuesday/Day -14

Admission or outpatient, dilantin blood levels will be checked and dose adjusted as needed to meet therapeutic range. Further adjustments if clinically indicated. Busulfan test dose administered at 6 a.m. as a single dose. The I/V dose is calculated as follows:

1. Body surface area (BSA) is calculated by the equation:

$$\text{BSA} = \frac{(\text{Actual body wt.(kg)} \times \text{height (cm)})}{3600}$$

Rev. 6/13/02

2. 22mg/m² I/V Busulfan will be given over 2 hours. Blood levels will be obtained with the first dose as per appendix 1 and will be performed at City of Hope.

Rev. 11/8/01

Wednesday/Day -13

Busulfan AUC will be calculated by standard methods available in the City of Hope Analytical Pharmacology Core Facility (APCF). The resulting AUC will be used to determine the dose required to achieve an AUC of 800 $\mu\text{M}^* \text{min}$ according to the following formula:

$$\text{Adj dose} = \text{Current dose} \times \frac{800\mu\text{M}^* \text{ min}}{\text{test dose AUC}}$$

Rev. 6/13/02

The maximum dose given will not exceed 32mg/m². There is no limit on dose reduction Busulfan dose will only be adjusted for AUC's <700 or >900 $\mu\text{M}^* \text{min}$.

Thursday/Day -12

The adjusted dose Busulfan dose will be given at 6 a.m. and blood levels will be repeated. Further dose adjustments will be performed if AUC >1000.

Friday/Day -11

Patient admitted to BMT or receive further dose of Busulfan in clinic.

Busulfan dosing restarted at 6 p.m. and is repeated every 6 hours for a total of 14 doses.

Tuesday/Day -7

Fractionated TBI will be given at 120 cGy per fraction for a total of 4 days for a total of 10 fractions for a total dose of 1200 cGy. See Appendix II.

Saturday/Day -3

VP-16 30mg/kg based on adjusted ideal body weight will be administered.

Tuesday/Day 0

PSC reinfusion/or BM infusion

See Appendix 3 for PSC Collection

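### Appendix III orders six donor G-CSF doses in its text (day -5 to day 0) but marks only five in its schema, so it is unclear whether a day 0 dose is given

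*Combined protocol and SAP*

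**What the plan says.** Appendix III sets out donor mobilisation and collection in two numbered items and a small schema.

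- **Item 1** orders G-CSF at 10 µg/kg/day "for 6 consecutive days from day -5 to day 0". It fixes the start by saying that the injection is given "daily beginning 5 days prior to day 0 (defined as the day marrow would ordinarily be given").
- **Item 2** restates the dosing as "Donors will receive -5 daily doses of G-CSF", again starting on day -5. The minus sign before the 5 is either a slip or the remains of a lost character.
- **The schema** has columns for days -5, -4, -3, -2, -1 and 0. The G-CSF row is marked on the first five and blank on day 0. The collection row reads "PBSC Collection | | | | | X | X", so it is marked on days -1 and 0.
- **Collection timing:** cells "will be collected in the afternoon of day -1 and reinfused on day 0". If that collection yields fewer than 5.0 × 10^6 CD34+ cells per kg of recipient weight, "a second collection will be performed the following morning and transfused on day 0".

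Elsewhere, section 5.1.2 allows either graft source ("Peripheral blood stem cells or bone marrow can be used"), and section 6.2 points to the appendix only for stem cell collection ("See Appendix 3 for PSC Collection"). The point is therefore confined to PBSC donors, even though item 1 is worded to cover every donor.

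**The concern.** Item 1 and the schema are both instructions for the same injections, and they differ on whether a donor is dosed on day 0. Staff who follow one will depart from the other. The injections may be given in the outpatient department or at home, so the number to prescribe and supply has to be settled beforehand.

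What is at stake is donor exposure. The consequence depends on the first collection:

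- **Adequate yield on day -1.** The protocol specifies no later collection, so a day 0 injection exposes the donor to drug for no collection in the plan.
- **Low yield on day -1.** A second collection follows on the morning of day 0. No injection time is stated, so it is not known whether a day 0 dose would come before or after it. An effect on the graft is possible, but only in this subgroup.

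**Working it through.** **Inputs, all from Appendix III:** daily dose 10 µg/kg; item 1 range, day -5 to day 0; schema marks, day -5 to day -1; first collection, afternoon of day -1.

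**Number of doses** (last day − first day + 1):

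- Item 1: 0 − (−5) + 1 = 6. This reproduces the six days that item 1 states, so item 1 agrees with itself and is not a simple miscount.
- Schema: −1 − (−5) + 1 = 5.
- Difference: 6 − 5 = 1 dose, on day 0.

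**Total exposure:**

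- Item 1: 6 × 10 = 60 µg/kg.
- Schema: 5 × 10 = 50 µg/kg.
- Difference: 60 − 50 = 10 µg/kg; 60/50 − 1 = 0.20, or 20% more under item 1.

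**Exposure by the first collection:** doses on days -5 to -1 are common to both readings, so 5 × 10 = 50 µg/kg under each, a difference of 0.

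**Absolute size of the extra dose.** The documents give no donor weights. Assuming a range:

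| Assumed donor weight | Day 0 dose |
|---|---|
| 50 kg | 10 × 50 = 500 µg |
| 70 kg | 10 × 70 = 700 µg |
| 90 kg | 10 × 90 = 900 µg |

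**Is the blank cell an artefact of PDF extraction?** Probably not. The collection row keeps its mark in the day 0 column, so the columns have not shifted. Item 2, if read as five doses starting on day -5, would also end on day -1, but its wording is damaged and the conflict does not depend on it.

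**Does anything reconcile the two?** Section 5.3 covers donor suitability only. Section 6.2 only refers the reader to the appendix. The study calendar in Appendix VI has no donor G-CSF row. Appendix III cites a practice manual for the collection procedure, not for G-CSF dosing. No text makes the day 0 dose conditional, and Appendix III carries no revision mark showing that one line replaced the other.

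**The case against.** The strongest reply is that the conflict is real but small. Dosing before the first collection is identical, section 12 has no donor endpoint, and the documents show no harm from a sixth dose at a daily level already ordered. On that view this is an editorial slip in an appendix. The facts in that reply are right, and they are why the point should not be rated higher. They do not make it merely editorial, because the line is a dosing order and correcting it changes what donors receive.

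Three further objections stand in part:

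- **Unseen text.** Consent pages were removed before review, and the practice manual is not available. A donor consent form might state the schedule. The claim that nothing reconciles the two lines therefore applies only to the text that can be seen.
- **Weak support from item 2.** A lost leading character could have left a range ending in 5, so item 2 cannot be used to prove five doses. The conflict rests on item 1 against the schema.
- **Which line was intended.** The documents do not say. Preferring the schema is a reasoned default, and the clinical team has to confirm it.

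It is also fair that changing only the days in item 1 would leave it addressed to every donor, marrow donors included.

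**Conclusion.** The conflict holds. Item 1 and the schema differ by one 10 µg/kg dose on day 0, which is 60 versus 50 µg/kg in total and 20% more under item 1. At assumed weights of 50 to 90 kg the extra dose is 500 to 900 µg. The difference by the day -1 collection is zero.

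The conclusion rests on the blank day 0 cell being genuine, which the intact collection row makes likely. The share of donors who need a second collection is not given, so the size of the subgroup in which the graft could be affected is unknown. No endpoint, sample size, stopping rule or planned analysis changes. It should be corrected because it governs what a donor is given; it does not threaten the trial's results.

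**What to change.** Confirm the intended schedule with the clinical team. Unless they want otherwise, change item 1 to five consecutive days, day -5 to day -1, and item 2 to five daily doses, so that both match the schema.

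If a day 0 dose is wanted, restrict it to donors whose day -1 collection is below 5.0 × 10^6 CD34+ cells/kg, state that it is given before the second collection, and show it as conditional in the schema. While item 1 is being edited, it would be sensible to address it to PBSC donors only.

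The cost is a correction to one line in each item, plus whatever amendment step the IRB requires for a change to a donor drug schedule. Sample size, timeline and analysis are unaffected.
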